The proposed additional participants will be drawn from the same woredas where participants were initially recruited, though new but from adjacent kebeles might be required in case adequate sample is not generated from the recruitment from the initial kebeles. An exception to the woredas is Tehuldere in Amhara where we have selected a complementary intervention woreda (Nineth) because after attempting to recruit participants from multiple kebeles, the recruitment yield was extremely low. Anecdotal reports suggest that there are existing MNCH programs in the woreda

which have been supporting women to adopt contraceptives and MNCH interventions. Since our eligibility criteria is AGYW who are not using a contraceptive method and who have not started ANC, this implies that it might not be feasible to recruit the desired sample from the same woreda even after exhaustively recruiting participants from all kebeles in the woreda. The total sample size for the survey therefore increases from 2,180 participants to 2,420 participants – 1,090 in Nigeria and 1,330 in Ethiopia. These numerical adjustments only affect the excess sample for non-pregnant girls since sample for pregnant girls that had been projected is preserved – we are topping up to maintain the earlier projection. In both countries, participants in the comparison arm will receive services as is expected based on the Ministry of Health guidelines in Ethiopia and Nigeria. Therefore, this group will be a partial control group.

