#### **Smart Pathways**

This component is layered on Smart Start. Smart Start targets married adolescent girls 15-19 and their spouses in Ethiopia in five regions: Oromia, Amhara, SNNPR, Sidama and South Western. Smart Start is implemented as part of the national Health Extension Program (HEP) through health

posts. Using a Smart Start discussion guide called a 'goal card' health extension workers (HEWs) engage married adolescent girls alone or with their husbands to discuss how the use of modern contraceptive methods to plan their families can facilitate financial planning and enhance the financial security of their families. This seamlessly creates relevance of contraceptives within a context where a direct conversation on modern contraceptives would be difficult. Smart Pathways (the MNCH component) is an expansion of Smart Start. Unlike Smart Start, it targets AGYW 15-24. In the communities, a team of trained FMOH-recognized community mobilizers consisting of members of the women development army (WDA) and Smart Start Navigators (SSNs) approach married adolescent girls from their communities and introduce them to Smart Start. Married girls who express interest to take up birth spacing are linked to HEWs who are working in the community or at health posts to receive the Smart Start intervention (pathway 1).

For girls who are ambivalent to receiving contraceptive counselling and services or those who intend to conceive soon, the trained mobilizers link them to an HEW who takes them through the Smart Pathways component for non- pregnant girls. When they land at the HEW, the HEW uses the Smart Pathways guide to discuss issues related to Preconception Care Counselling and early ANC initiation (pathway 2). For girls who have missed their periods or suspect that they are pregnant, the trained mobilizers link them to health centres or health posts where HEWs or midwives take them through a seven-step process that covers pregnancy testing, building demand for ANC, the benefits and components of ANC, danger signs of pregnancy, smart nutrition, preparation for delivery and post-partum family planning (pathway 3). Girls in Pathway 2 who conceive are referred to navigate through pathway 3 when that time comes. The three pathways are illustrated in Figure 1.

As married pregnant AGYW navigate through ANC, they are offered services based on the Ethiopia Federal Ministry of Health antenatal care guidelines (Ministry of Health of Ethiopia, 2022).

[figure not shown]

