**Table 1: Inclusion and exclusion criteria**

Group	Inclusion	Exclusion
Married AGYW (survey)	
 
• Aged 15 to 19 (Nigeria) and 15-24 (Ethiopia)
 
• Married
 
• Resident in a study site
 
• If pregnant should be at most 24 weeks gestation
 
• If not pregnant, at risk of pregnancy (not using a contraceptive method at the time of the survey with or without intend to conceive)
 
• Consent to participate in the study
 
	
 
• Married AGYW, aged 15-19 (Nigeria) or 15-24 (Ethiopia) who decline to give consent
 
• If pregnant, has an advanced pregnancy (<math>\geq</math> 25 weeks gestation)
 
• If not pregnant, currently using a contraceptive method
 

Married AGYW (FGDs and IDIs)	
 
• Married and aged 15 to 19 (Nigeria) and 15-24 (Ethiopia)
 
• Currently pregnant or in the post-partum period (after recent delivery)
 
• Participated in the full MNCH components of MMA or Smart Start
 
• Consent to participate in the study
 
	
 
• Married AGYW aged under 15 or over 19 (Nigeria) or over 24 (Ethiopia)
 
• Not pregnant or not in post-partum period
 
• Did not participate in MNCH component
 
• Decline to consent
 

Husbands of AGYW (Nigeria only)	
 
• Male aged 18 years and over
 
• Husband of an AGYW aged 15 to 19
 
• Has participated in husband sessions (at the community or facility) of the MNCH component
 
• Consent to participate in the study
 
	
 
• Males under 18 years
 
• Did not participate in the husband sessions for the MNCH component
 
• Husband who decline to give consent
 

Health worker / community health mobilizer	
 
• Employed as a health worker (can be nurse, midwife, etc.) or mobilizer (female mentor, member of WDA or MIPCA) within the study site.
 
• Served at the facility or community for this role for six or more months.
 
• Provides services along the MNCH continuum of care (e.g., ANC, delivery, PPFP, etc.)
 
	
 
• Recently employed health worker or mobiliser (< 6 months)
 
• Not familiar with MNCH or FP services
 
• Unwilling to consent
 

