#### 2.4.1 Recruitment of married AGYW

Different recruitment procedures will be used for the Quantitative survey and the Qualitative component.

**(i) For the quantitative survey** in both Nigeria and Ethiopia, the research team will leverage already existing trained mobilizers (female mentors in Nigeria & members of WDA and female SSNs) to perform recruitment procedures. The mobilizers will be trained to identify and recruit AGYW from the community guided by a recruitment script. The mobilizers in Nigeria and Ethiopia are familiar with their communities and will approach potential participants directly by face-to-face contact during their routine household visits, in clinics and/or during community gatherings.

When a mobilizer approaches a married AGYW, she will ask her for verbal consent to speak to her in private. She will ask her the four screening questions (in the recruitment script) after providing brief details about the nature of the evaluation. If the potential participant is eligible and has expressed interest to participate, the mobilizer will obtain the contact details (name, phone number and details of residential address) and record these in a recruitment confidential contacts' list (**Appendix Q attached to the submission**). Details of residential address are collected because a substantive number of AGYW in these locations might not own or have access to a phone as reported in recent surveys – 40.2% in Ethiopia and 6-21% in northern Nigeria (Krug et al., 2021a, 2021b). These lists will be passed to a data collector (research assistant) working in the study locality on a daily basis. The AGYW will also be notified that they should expect a call or a visit from a female enumerator at a future date. During the period when we execute a modification to increase the number of pregnant girls in Amhara, South, and Central Ethiopia and Sidama, recruiters will only identify, approach and invite pregnant girls only. To do so, they will be trained not to field the screening question on contraceptive use (question 3) in the recruitment script - the rest of the procedures and questions will be fielded as they are. During this period, they will only capture contact details of eligible pregnant girls in the confidential recruitment contact lists.

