## **2.6 SAMPLE SIZE ESTIMATION AND SAMPLING PROCEDURES**

The sample size for the quantitative survey is estimated using a two-sided Wald Z-test using GEE methods, accounting for repeated measures and clustering within groups and assumes no change of the estimate for the primary outcome for the study within the comparison group. The primary outcome will be a binary measure, which documents whether the AGYW has met criteria for 'comprehensive' knowledge of what is needed at conception to attain a healthy pregnancy. It will be estimated from a composite measure made from a combination of questions assessing AGYW about their knowledge about behaviors (proper nutrition, screening tests and treatment for HIV and sexually transmitted infections, use of prenatal vitamins, and avoidance of harmful substances). These questions are curated from a systematic review conducted in Ethiopia on the knowledge of preconceptual care and which is also relevant for Nigeria(Ayele et al., 2021). This study established a pooled estimate of good knowledge of preconceptual care of 30.9%. In our study, an AGYW will be comprehensively knowledgeable if she responds to the affirmative to all the questions. The questions will be fielded at the time of recruitment and repeated 3 months later.

To detect an effect size of 10% (between recruitment and 3 months later assuming no change in the comparison group), with a power of 80% at the 95% confidence level (two-sided), we would need a sample size of 991 participants in each country equally split between the comparison and intervention group. This assumes an adjustment of 10% for non-response and a design effect of 1.2. Appendix R (page 57) summarizes sample sizes with different scenarios of estimated effect sizes. We adjust this sample upwards by 10% to account for attrition that might occur between recruitment and the follow-up after 3 months to arrive at a sample size of 1,090 which when split between the groups would be 545 AGYW. Cumulatively for Nigeria and Ethiopia, the final sample size would entail 2,180 participants. This sample is increased by 240 to 2,420 to account for recruitment adjustments for Ethiopia.

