A two-group repeated measures design with a binary response and with 2 measurements for each subject will be used to test whether there is a difference in group slopes. The comparison will be made using a Wald Z-test using GEE methods. The repeated measurements of each subject will be made at 2 times and using an autoregressive correlation structure (AR1). The initial proportions  $P1(0)$  and  $P2(0)$  are estimated at 0.3 based on estimates in the literature (preconception care knowledge).  $P2(1)$  proportion assumes no change in the primary outcome over the course of the intervention. Estimates are adjusted by 10% missing/non-response rate and a design effect of 1.2 to account for within community or group clustering.

Table 2 shows estimated total sample sizes for the primary and secondary target populations included in this study.

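### Programme mobilisers recruit for the survey while the component is running, and nothing requires the baseline interview to precede a girl's first MNCH session, so some intervention-arm baselines can be post-exposure and pull the difference-in-difference toward zero.

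*Protocol*

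**What the plan says.** **Who recruits.** Section 2.4.1 uses existing mobilisers: female mentors in Nigeria, and Women Development Army members and Smart Start Navigators in Ethiopia. They "will approach potential participants directly by face-to-face contact during their routine household visits, in clinics and/or during community gatherings". After listing, "The AGYW will also be notified that they should expect a call or a visit from a female enumerator at a future date".

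**Who brings girls to the intervention.** Section 1.3 gives the same cadres that task. In Nigeria, female mentors mobilise girls to the LFH sessions and moderate them. In Ethiopia, for girls who are ambivalent about contraception or intend to conceive soon, "the trained mobilizers link them to an HEW who takes them through the Smart Pathways component".

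**When.** The Summary (Context) places the evaluation in parallel with implementation. Section 2.2 locates the intervention arm where the component is already offered.

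**Who is eligible.** The survey row of Table 1 covers age, marriage, residence ("Resident in a study site"), gestation, contraceptive use and consent. Participation in the MNCH component appears only in the qualitative rows for girls and husbands, where it is required. The Summary (Methods) separately describes the eligible girls as not using contraception and not yet in ANC. The ANC part is not in Table 1.

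**How the effect is measured.** Section 2.6 asks the knowledge questions at recruitment and 3 months later. Section 2.9.1 analyses the outcomes as a difference-in-difference, with a GEE Wald test of the difference in slopes for the primary outcome.

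**The concern.** A difference-in-difference needs a baseline taken before exposure. Here, a girl in an intervention area can attend preconception counselling or an LFH session, be listed by the mobiliser who sent her there, and then give a baseline interview that counts as pre-intervention. Whatever she has already learned raises the intervention-arm baseline and is subtracted from the measured change.

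Preconception counselling bears directly on the primary outcome, which is knowledge of what is needed at conception. Exposure to the new sessions before baseline can occur only where they are offered, so the comparison arm does not offset it.

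An effective component could therefore look weaker than it is. Without a date of first attendance, the analysis could neither detect nor correct this. The limitations in section 2.11 do not mention it.

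**Working it through.** **Inputs from section 2.6.** Test and power: "with a power of 80% at the 95% confidence level (two-sided"). Effect: "To detect an effect size of 10% (between recruitment and 3 months later assuming no change in the comparison group"). Starting proportions in both arms "are estimated at 0.3 based on estimates in the literature (preconception care knowledge"). Design effect 1.2, non-response 10%, 1:1 split, then 10% more for attrition. The AR1 correlation is not given; I assume 0.5.

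**Step 1: reproduce the planned size.** For a logit GEE slope test with two time points,

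n per arm = (1.960 + 0.842)² × V / D²,

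where D is the difference in logit slopes. V sums, over both arms, 1/(p₀q₀) + 1/(p₁q₁) − 2ρ/√(p₀q₀p₁q₁).

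- With 0.30 to 0.40 against 0.30 to 0.30 and ρ = 0.5: D = 0.442 and V = 9.236.
- n = 7.849 × 9.236 / 0.442² ≈ 371.3 per arm.
- 2 × 371.3 × 1.2 / 0.9 ≈ 990, against 991 stated. 991 × 1.1 = 1,090, as stated.

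The planned size rests on both arms starting at 0.30.

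**Step 2: let a fraction f of the intervention arm be exposed before baseline.** The documents do not give f. Let exposed girls already hold a share g of the 10-point gain, and let the arm reach 0.40 at 3 months. The baseline becomes 0.30 + 0.10·f·g, and the expected difference-in-difference is 10(1 − f·g) points.

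**Step 3: power.** Power = Φ(D/√(V/n) − 1.96).

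- At 1,090, with 10% non-response and 10% attrition: n = 1,090 × 0.9 × 0.9 / (2 × 1.2) = 367.9 per arm.
- At Ethiopia's 1,330 (treating 661 and 669 as equal arms): n = 1,330 × 0.81 / 2.4 = 448.9 per arm.

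Example, f = 10% and g = 1 at 1,090: baseline 0.31, D = 0.395, V = 9.190, √(9.190/367.9) = 0.158. Then 0.395/0.158 − 1.96 ≈ 0.54, and power ≈ 70%.

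| f | Gain held at baseline | Expected DiD (points) | Power at 1,090 | Power at 1,330 |
|---|---|---|---|---|
| 0 | none | 10.0 | 80% | 87% |
| 10% | full | 9.0 | 70% | 79% |
| 20% | full | 8.0 | 60% | 68% |
| 30% | full | 7.0 | 49% | 57% |
| 10% | half | 9.5 | 75% | 83% |
| 20% | half | 9.0 | 70% | 79% |
| 30% | half | 8.5 | 65% | 74% |

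**Step 4: dependence on ρ.** At 1,090 with f = 20% and the full gain held, power falls from 65% to 46% at ρ = 0.3 and from 95% to 81% at ρ = 0.7. The lost points in the estimate do not depend on ρ.

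**Step 5: who is left unprotected.** The no-ANC-yet criterion, if applied, removes pregnant girls who have entered ANC. It does not remove pregnant girls who attended a session before starting ANC, or non-pregnant girls who had counselling or LFH sessions. Non-pregnant girls were 445 of the first 683 enrolled in Ethiopia (445/683 = 65%).

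**The case against.** Several points on the other side have force.

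- **The ANC criterion.** In Nigeria, mobilised girls who test positive go on to routine ANC, so many exposed pregnant girls would fail it. It protects part of the sample. But it is absent from Table 1 and does not reach the exposures in step 5.
- **The top-up.** A reader might infer that the Ethiopian top-up is the worst-affected group, because "The proposed additional participants will be drawn from the same woredas where participants were initially recruited". The documents do not support that. The top-up takes pregnant girls only, the group the ANC criterion protects most. It may use adjacent new kebeles, and one Amhara woreda is supplemented by a new one.
- **The interval before interview.** Lists pass to data collectors daily, and a home visit can become the interview on the spot. This shortens the gap after listing for some girls. It sets no maximum, and does nothing about attendance before listing.
- **The full-gain assumption.** LFH is four sessions over four weeks, and the outcome needs every question answered affirmatively. A partial attender may hold little of the gain, so the full-gain rows are a worst case.
- **The comparison arm.** It already receives MMA or Smart Start, LFH covers nutrition, and section 2.11 concedes some overlap in content. So not all early learning is confined to one arm. Exposure to the new component itself is.
- **Material not shown.** The recruitment scripts have four screening questions, of which the text identifies only the one on contraceptive use. The scripts or questionnaire could ask about earlier sessions. Nothing in the protocol text or Table 1 says so.

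**Conclusion.** The gap is real and worth closing. Followed as written, the plan can enrol intervention-arm girls who have already had MNCH sessions and count their interview as a pre-intervention baseline. The bias is toward zero if exposed girls have already gained knowledge and gain less afterwards. It matters most for non-pregnant girls.

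If exposed girls hold the full gain, each 10% exposed removes 1 of the 10 points; if they hold half, it removes 0.5. At 1,090 and ρ = 0.5, power at 10% to 30% exposed runs from about 70% down to 49% (full gain) or 75% down to 65% (half gain). The exposed share, the gain held and ρ are all assumptions.

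Two stronger readings go too far. The documents do not show that any baseline was in fact contaminated, only that nothing prevents it. And the top-up's share of the Ethiopian intervention arm in Table 2, 116/661 = 17.5%, is not an estimate of exposure.

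**What to change.** 1. Reconcile the no-ANC-yet criterion in the Summary with Table 1, so that one eligibility statement governs the survey.
2. For all remaining recruitment, require the baseline interview to precede the girl's first expanded-LFH or Smart Pathways session, or screen out girls who have already attended one. State this in Table 1 and the recruitment script. It is a survey eligibility rule and does not change when sessions are offered.
3. At the 3-month interview, ask every girl whether and when she first attended. This also covers those already enrolled.
4. Repeat the primary analysis without girls whose first session preceded baseline.

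**Cost.** One screening item, one or two 3-month questions and one extra analysis. Section 2.8.1 requires an ethics amendment for added questions. Recruitment yield will be slightly lower. The exclusion also acts on the intervention arm only, may remove its most engaged girls, and gives later recruits different eligibility from those already enrolled. In a non-randomised comparison this can create imbalance, so the exclusion analysis should be a sensitivity analysis reported beside the full-sample result, not a replacement for it.

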#### **2.4.2 AGYW's husbands in Nigeria**

Husbands will be recruited from the same communities as the primary target group. For the IDIs with husbands, recruitment will be implemented through male IPCAs who are facilitating the MNCH components that involve husbands. They are also familiar with the communities they are working in and will be trained to identify potential participants based on the specific criteria and specific instructions given on the caliber of husbands to select. Male IPCAs will conduct purposive sampling to select husbands from the program activity registers and reach each one by one. Only husbands with phone contacts in the activity records could be selected. When male IPCAs have reached the required number of husbands, they will start contacting them, on phone (only). The male IPCAs, while guided by a recruitment script, will provide brief information about the study to the selected husbands (from the attendance records they maintain) who have been involved in the intervention and obtain their verbal consent. Husbands who express interest to participate will then be invited to respond to a few screening questions to determine eligibility. Eligible husbands will be asked to share their contact details which male IPCAs will document on the confidential contact lists. The remaining steps of the recruitment procedures employed for the AGYW IDIs (step 2 and 3) will be replicated for husband IDIs once the confidential contact lists have been developed except that a male qualitative researcher will execute these procedures.

#### **2.4.3 Health workers and mobilizers**

This group will be approached by the research team through contacts shared by the project field team. These contacts will be shared with the qualitative researcher who will execute the bulk of recruitment procedures. A brief description of the evaluation will be explained to the selected potential participants, screening questions fielded and those who express interest invited to propose a date and time for the KII.

### **2.5 CAPTURING OF PERSONAL-IDENTIFYING INFORMATION (PII) FOR RECRUITMENT**

As described earlier, PII will be collected as part of the recruitment process. Mobilizers, male IPCAs and field program staff will provide the research team with the name, physical address or contact details of potential participants. In Nigeria, the recruiters working under SFH will work closely with Viable Knowledge Masters' (VKM) personnel and for Ethiopia recruiters under MOH Ethiopia will work with personnel from Deep Dive Research and Consulting PLC. VKM and Deep Dive Research and Consulting PLC will be the primary recipients of the PII on behalf of PSI and SFH. The PII will be used exclusively for the purpose of inviting participants to participate. The in-country lead investigators will be responsible for ensuring that this information is stored securely (in a secure location – locked room by VKM and Deep Dive Research and Consulting PLC offices) until recruitment has happened. Participant trackers for the survey will be hosted in PSI SharePoint

Folder and the access to these files will be restricted to specific VKM and Deep Dive Research and Consulting PLC staff. The PI will authorize VKM and Deep Dive Research and Consulting PLC to destroy the PII immediately after recruitment has been completed. These data will never be linked to data collected as part of the study, nor shared beyond authorized members of the evaluation team. In-country Lead investigators will oversee the handling and storage of the PII collected for recruitment.

